Immunoglobulin(s); IgG4-RD RI = IgG4-RD Responder Index; IP = investigational product; SAE = serious adverse event; V = visit.														
Note: On days of IP administra	ation, all p	procedure	s and bloo	od sampli	ng, excep	t for		must be	collected	before IF	administ	tration.		
Vital signs obtained as per Section 7.1.1.5.														

Table 4 Randomized-Controlled Period Assessments and Procedures

d Subjects who have indicated their intent to withdraw consent during the RCP should be asked to complete an EDV visit.

e Premedication will be administered approximately 30-60 minutes prior to each IP infusion (see Section 7.1.1.4). If IP administration at Visit 9 (Day 183) is unavoidably delayed, for example due to COVID travel restrictions, the dosing visit may be delayed upon discussion and agreement with the Sponsor. Adjustment of the timing of the subsequent OLP IP doses will be discussed on a case-by-case with the Sponsor. If a subject discontinues IP during the RCP, they should complete all RCP visits. If they do not subsequently enter the OLP, they should then enter the SFUP (Section 6.2.4).

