6.2.3 Schedule of OLP Assessments and Procedures

6.2.3.1 Eligibility for OLP

Subjects eligible for the OLP must:

- 1. Have completed the RCP Week 52 visit (end of RCP).
- 2. Must not have had IP discontinued for any of the following safety reasons:
 - Anaphylaxis or a serious hypersensitivity reaction that occurred within 7 days after IV dosing and cannot be attributed to another known allergen exposure (see Appendix B).
 - Any adverse event (AE) or significant laboratory abnormality that, in the opinion of the Investigator, Sponsor, or SDMC, warrants discontinuation of dosing.
 - Any life-threatening (Grade 4) infection.
 - Any event of sepsis or febrile neutropenia.
 - Any infection listed as either a definite or probable opportunistic infection in Appendix A.
 - Any Grade 3 IRR.
 - Any Grade 4 serious adverse event (SAE).
 - Pregnancy or a decision to become pregnant.
 - Malignancy.
 - Absolute neutrophil count < 800 cells/ μ L confirmed by repeat testing.
 - Determination that the subject was ineligible for study participation and continuation of IP could pose a safety risk to the subject in the judgment of the Investigator or Sponsor.
 - Significant noncompliance with the study protocol, as judged by the Investigator or Sponsor.
 - Receipt of any B cell-depleting therapy (eg, rituximab, ocrelizumab, obinutuzumab, ofatumumab, commercially available inebilizumab).
- 3. Have completed a 28-day washout period after discontinuation of non-B cell-depleting, non-GC immunosuppressive therapy initiated during the RCP, if relevant.
- 4. Receive Dose 1 in the OLP within the window of 1-38 days after the RCP Week 52 visit (the final visit for the RCP and the first visit for the OLP cannot occur on the same day).
- 5. Have a planned taper of GCs to discontinuation by 8 weeks after OLP Dose 1, if receiving GC at the time of OLP entry.

To maintain the every-6-month dosing of IP, subjects should enroll in the OLP and be dosed as soon as is feasible after completion of the RCP. All SAEs and AEs that occur between the end of the RCP and start of the OLP must be collected at OLP Visit 1. Investigational product discontinuation rules apply during the OLP (Section 6.4.1).

Table 5 summarizes the schedule of procedures for the OLP.

Study Period					Open-Lal	oel Perio	d						
OLP Visit Number	OLP V1	OLP V2	OLP V3, V4	OLP V5	OLP V6, V7	OLP V8	OLP V9, V10	OLP V11	OLP V12, V13	OLP V14	OLP V15, 17, 19, 21	OLP V16, 18, 20,	OLP V22/EDV

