# **3** STATISTICAL METHODS

#### 3.1 General Considerations

The efficacy endpoints will be summarized at scheduled visits during RCP and OLP, respectively. For subjects in the OLP, the efficacy may also be summarized over the combined RCP and OLP to characterize the durability of the treatment effect, if applicable. And the summary over the combined RCP and OLP will be based on the subjects who received any dose of inebilizumab.

The safety endpoints will be summarized for the RCP, OLP, combined RCP and OLP, and SFP, respectively.

All efficacy analyses described below apply to the RCP unless stated otherwise.

The analyses with a treatment policy strategy will include all data captured during the 52week RCP, defined as the period after first IP administration at Visit 2 (Day 1) to the conclusion of the scheduled last RCP visit at Visit 15 (Week 52), inclusive, up to but not beyond Day 1 of the OLP.

As sensitivity analyses, the analyses applying the while-on-treatment strategy for safety endpoints will include all data captured while subjects are on treatment, defined as the period after randomization at Visit 2 and 6 months (183 days) after the last treatment during the RCP, inclusive.

All statistical calculations will be primarily performed using SAS® System Version 9.4 or higher. Tabular summaries will be presented by treatment arm. Categorical data will be summarized by the number and percentage of subjects in each category. Continuous variables will be summarized by descriptive statistics, including number of observations, mean, standard deviation, median, Q1, Q3, minimum, and maximum. Data listings will be sorted by treatment group and subject number.

Where appropriate, model-based estimates will be presented with their two-sided 95% confidence interval (CI) and p-values. Unless otherwise stated, nominal p-values will be reported and rounded to 4 decimal places.

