#### **3.6.1** Adverse Events

Adverse event and serious adverse event collection begins after the subject signs the informed consent document and continues until the end of study visit. AEs and SAEs collected during the RCP will be analyzed using a treatment policy strategy (which includes all data captured during the RCP), and a while-on-treatment strategy (which includes all data captured while subjects are on treatment). AEs and SAEs collected during the OLP, SFP and combined RCP and OLP, will be analyzed using a treatment policy strategy. For subjects who withdraw from the study, data collected up until the last visit will be included. Table 5 defines TEAEs for different analyses.

RCP (Treatment Policy)	RCP (While-on- treatment)	OLP	Combined RCP and OLP (Any Inebilizumab Analysis Set)	SFP
A TEAE is defined as any AE with onset date on or after the first RCP IP dose, and on or before the end of RCP.	A TEAE is defined as any AE with onset date on or after the first RCP IP dose, and on or before 6 months (183 Days) after the last RCP dose.	A TEAE is defined as any AE with onset date on or after first OLP IP dose and up to the end of OLP (prior to the SFP entry if a subject enrolled into SFP).	A TEAE is defined as any AE with onset date on or after the first inebilizumab dose (either RCP or OLP) and up to and including the day prior to the end of RCP (if a subject didn't enroll into OLP) or the end of OLP (i.e., the day prior to the SFP entry, if a subject rolled over to OLP).	TEAE is defined as any AE with onset date after the last IP dose during the study.

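### The RCP while-on-treatment adverse-event window and its person-time do not stop at OLP Dose 1, so some events after a former placebo subject's first inebilizumab infusion can be tabulated under placebo

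*SAP*

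**What the plan says.** The SAP defines two safety windows for the RCP.

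- **Treatment policy.** SAP 3.1 runs the period to the Week 52 visit, "inclusive, up to but not beyond Day 1 of the OLP". The corresponding column of Table 5 (SAP 3.6.1) limits events to those with onset after first dosing "and on or before the end of RCP".
- **While-on-treatment.** SAP 3.1 presents this as a sensitivity analysis for safety and runs it to "6 months (183 days) after the last treatment during the RCP, inclusive". Table 5 takes events with onset "on or before 6 months (183 Days) after the last RCP dose". Neither place mentions the OLP. Protocol 9.1 defines the period in the same way, also without a cap.

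The while-on-treatment person-year formula, further on in SAP 3.6.1, counts from the first RCP dose to 183 days after the last one. It has no cap either.

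The schedule comes from the protocol. Table 4 puts the last RCP infusion at Visit 9, Day 183 with a window of 5 days either side, and the Week 52 visit at Day 365 with 7 days either side. Section 6.2.3.1 allows OLP Dose 1 from 1 to 38 days after Week 52 and says that "subjects should enroll in the OLP and be dosed as soon as is feasible after completion of the RCP". If Visit 9 dosing is unavoidably held up, footnote e to Table 4 says "the dosing visit may be delayed upon discussion and agreement with the Sponsor", and then that the timing of later OLP doses will be settled with the Sponsor case by case.

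Under SAP 2.2 both arms receive inebilizumab on OLP Day 1. Former placebo subjects receive it again on OLP Day 15.

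**The concern.** The two windows are treated differently. The authors saw that the treatment-policy period could run into the open-label period and wrote a stop. They wrote none for the other window, which is anchored to a dose that can fall close to 183 days before the OLP begins.

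For a subject randomized to placebo, OLP Dose 1 is the first exposure to inebilizumab. If it falls inside the RCP while-on-treatment window, an AE that follows it meets the RCP definition and goes in the placebo column. It also meets the OLP definition in Table 5, which starts at the first OLP dose, so the same event appears in two period tables. The same days enter two person-time totals.

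Even a one-day overlap is relevant, because that day is the day of the infusion. Infusion-related reactions are an AE of special interest here, and Protocol 2.1.5.3 reports that in Study 1155 they were most common with the first infusion. A placebo-controlled table should not contain events that follow active drug in the placebo arm.

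**Working it through.** **Inputs.** Last RCP dose D: Day 183, range 178 to 188 (Protocol Table 4). Week 52 visit W: Day 365, range 358 to 372 (Protocol Table 4). Gap G from Week 52 to OLP Dose 1: 1 to 38 days (Protocol 6.2.3.1). Window length: 183 days (SAP 3.1 and Table 5).

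**Formulas.** Window end = D + 183. OLP Dose 1 day = W + G. Overlap in days, counted inclusively = max(0, D + 183 − (W + G) + 1).

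**Nominal schedule.** Window end = 183 + 183 = Day 366. With G = 1, OLP Dose 1 = 365 + 1 = Day 366, so the overlap is 366 − 366 + 1 = 1 day. With G = 2 it is 366 − 367 + 1 = 0. Nominal visits therefore give an overlap only for a gap of exactly one day.

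**Within the visit windows, shortest gap (G = 1).**

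| Last RCP dose | Week 52 visit | Window end | OLP Dose 1 | Overlap (days) |
|---|---|---|---|---|
| 178 | 358 | 361 | 359 | 3 |
| 183 | 358 | 366 | 359 | 8 |
| 188 | 358 | 371 | 359 | 13 |
| 188 | 365 | 371 | 366 | 6 |
| 178 | 365 | 361 | 366 | 0 |
| 188 | 372 | 371 | 373 | 0 |

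The maximum is 13 days. A subject whose last RCP dose was on Day 15 has a window closing on 15 + 183 = Day 198, long before the OLP, so only subjects dosed at Week 26 are exposed to the problem.

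**Share of subjects with any overlap.** The documents give no distribution of visit timing. Assume every combination of D (11 values), W (15 values) and G equally likely, and count the combinations with overlap:

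- G from 1 to 7: 395 of 11 × 15 × 7 = 1,155, or 34%, with mean overlap 4.3 days among those affected.
- G from 1 to 14: 451 of 2,310, or 20%, mean 4.0 days.
- G from 1 to 38: 451 of 6,270, or 7%, mean 4.0 days.

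Only the last range is documented. The shorter two represent the instruction to dose early, but their limits are assumptions.

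**Ceiling on the number of placebo subjects.** If all 80 planned placebo subjects received the Week 26 infusion and entered the OLP, the counts would be 80 × 0.072 = 5.8, 80 × 0.195 = 15.6 and 80 × 0.342 = 27.4. Fewer will do both, so the true counts are lower.

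**Rough yield of infusion reactions.** Study 1155 reported infusion reactions in 9.2% of inebilizumab subjects over its randomized period, which had two infusions. Treating 9.2% as a first-infusion rate is generous. It gives 5.8 × 0.092 = 0.5 to 27.4 × 0.092 = 2.5 subjects with a reaction placed in the placebo column. Other AEs during the overlap would add to this.

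**Person-time.** Nominal, one-day gap: 366/365.25 = 1.002 years uncapped, against 365/365.25 = 0.999 if capped the day before OLP Dose 1. Extreme in-window case: 371/365.25 = 1.016 against 358/365.25 = 0.980.

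**The case against.** The best defence is that the sentence introducing Table 5 already restricts the analysis to AEs collected in the RCP. Protocol 4.1 ends the RCP for each subject at the Week 52 visit, the column is labelled RCP, and AEs arising after the RCP are collected at OLP Visit 1. On that reading an event after OLP Dose 1 never enters the table.

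This makes the text ambiguous but does not settle it. The same sentence separates the two strategies: treatment policy takes all RCP data, while the other takes all data while subjects are on treatment. Only the treatment-policy column then names the end of the RCP as its limit. The person-year formula is explicit and uncapped, so a programmer who limits events by the introductory sentence and follows that formula would have a numerator and a denominator covering different periods.

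Other parts of the defence stand:

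- The bounded treatment-policy summary is unaffected.
- The risk difference that SAP 3.6.1 describes for AEs of special interest refers to cumulative incidence by Week 52.
- Inebilizumab-arm subjects are also infused on OLP Day 1, so the overlap can add events to both columns.
- Study 1155 reported infusion reactions in 9.2% of inebilizumab and 10.7% of placebo subjects in its RCP, which gives no ground for expecting a large difference between arms.
- The repeated event sits in two separate period tables; it is not counted twice within one.

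**Conclusion.** The gap in the definition is real. Following SAP 3.1, Table 5 and the person-year formula as written can put AEs that follow a former placebo subject's first inebilizumab infusion under placebo in the RCP while-on-treatment tables, and also in the OLP tables. The overlap is 1 day on nominal visits with next-day OLP dosing, none on nominal visits with a longer gap, and at most 13 days within the visit windows. About 7% of OLP entrants dosed at Week 26 are affected over the documented gap range, and 20% to 34% over the assumed shorter ranges. All three shares rest on the uniform-timing assumption. The practical effect on a sensitivity analysis is probably small.

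Three stronger readings are tempting, and the documents do not support them:

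- A reader might infer that OLP Dose 1 falls inside the window for every fully dosed subject on the nominal schedule. It does so only for a gap of exactly one day.
- A reader might infer that a postponed Visit 9 infusion produces weeks of overlap. A Sponsor-agreed delay could lengthen it, but footnote e gives no length and allows OLP timing to be adjusted. The amount is unknown.
- A reader might infer that the error makes inebilizumab look safer. Because both arms are infused on OLP Day 1, neither the size nor the direction of any bias is established.

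**What to change.** In SAP 3.1, in the while-on-treatment column of Table 5, and in the while-on-treatment person-year formula of SAP 3.6.1, end both the event window and the person-time at the earliest of:

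- the last RCP dose plus 183 days;
- the end of the subject's RCP participation;
- the day before OLP Dose 1.

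All three places must change together. Capping the events but not the formula would create a mismatch in the rates per 100 person-years. The second limit also stops person-time from accruing after a subject has left the RCP. With these limits the overlap is zero in every scenario above.

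The cost is a few lines of SAP text and the matching programming specification. No new data are needed, and neither the treatment-policy tables nor any efficacy analysis changes.

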• Inebilizumab group: Subjects will receive an infusion of inebilizumab 300 mg IV on Day 1, Day 15, and at Week 26.

• Placebo group: Subjects will receive an infusion of placebo on Day 1, Day 15, and at Week 26.

Both treatment groups will receive open-label IV methylprednisolone 100 mg (or equivalent), diphenhydramine 25-50 mg or equivalent, and paracetamol/acetaminophen 500-650 mg or equivalent, 30-60 minutes prior to each IV infusion for prophylaxis of infusion reactions.

Both treatment groups will continue to receive open-label GCs, from local commercial supply, during an 8-week taper regimen (2 weeks each at 20, 15, 10, and 5 mg/day of prednisone or equivalent), representing completion of the GC taper regimen following treatment for their recent flare (Section 7.2.1).

During the 52-week RCP, subjects will attend monthly visits for study assessments and procedures (Section 546.2.2. Suspicion of flare will trigger diagnostic assessments by the Investigator (Section 6.3.2.1). The Investigator will determine if the event meets protocol -defined criteria for flare, and, independent of the flare determination, will decide if the event requires treatment. The same data reviewed by the Investigator will also be evaluated by a central, independent, and blinded AC that will determine whether protocol-defined flare criteria are met (Section 6.3.2.1).

The end of the RCP is defined, per subject, as the date of completion of the Week 52 RCP visit. All subjects should be followed through the end of the RCP. In exceptional circumstances and with agreement of the medical monitor, particular study visits or procedures may be performed remotely (via teleconference, video conference, or similar) if the subject is not able to physically attend the clinic for that visit or procedure (eg, due to COVID-19 restrictions or for other reasons). Such instances will not be considered protocol deviations. If virtual visits must occur, subjects should obtain safety laboratory testing locally when feasible.

A subject who decides to withdraw from the RCP should be asked to complete the final RCP visit (early discontinuation visit [EDV], Table 4) for safety follow-up whether or not they will permit phlebotomy.

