6.3.3 Safety Assessments

Clinically important abnormalities in vital signs, body weight, physical examination, laboratory parameters, and ECGs will be recorded as AEs or SAEs.

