#### 3.4.3 Study Drug Exposure

Study drug exposure, which includes number of doses, dose amount and dose amount adjusted for weight (mg/kg) of the study drug, and durations of the study drug exposure, will be summarized for RCP, OLP, and Any Inebilizumab exposure by treatment group. In addition, treatment compliance will also be summarized for RCP.

The amount of study drug exposure: If entire dose was administered, the dose amount (mg) at a specific visit will be either 0 or 300 mg depending on what treatment the subject had received; if a subject received partial dose at a dosing visit, then the amount of study

drug at that dosing visit will be estimated based on the actual volume administered. For example, if a subject receives 175 mL (instead of the full 250 mL), the dose amount (mg) will be estimated as =  $300 \text{ mg} \times 175 \text{ mL} / 250 \text{ mL} = 210 \text{ mg}$  provided the subject received inebilizumab.

Treatment compliance for an individual subject = [Total number of doses received]/ [Total number of doses planned per protocol]  $\times 100\%$ .

The definition of duration of study drug exposure and person-years of exposure is outlined in Table 4.

RCP	OLP	Combined RCP and OLP (Any Inebilizumab Exposure)	
	Duration of study drug exposure		
Last RCP dose date $-1^{st}$ RCP dose date $+90^{a}$	Last OLP dose date $-1^{st}$ OLP dose date $+90^{a}$	Last inebilizumab dose date – 1 st inebilizumab dose date + 90 a	
Person-year definition for individual subject b			
$\begin{array}{c c} (\text{Date of last RCP day} - 1^{\text{st}} \text{ RCP dose} \\ \text{date} + 1)/365.25 \end{array} \\ \begin{array}{c c} (\text{Date of last OLP day} - 1^{\text{st}} \text{ OLP} \\ \text{dose date} + 1)/365.25 \end{array} \\ \begin{array}{c c} (\text{Date of last study day in RCP or} \\ \text{OLP} - 1^{\text{st}} \text{ inebilizumab dose date} + 1)/365.25 \end{array} \\ \end{array}$			
a Based on 5 half-lives (18 days) determined from previous late-stage clinical trials			
b Total person-years will be calculated as the sum of the person-years for individual subject			

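### SAP Table 5 ends the combined-period TEAE window one day too early for inebilizumab-treated subjects who do not enter the OLP

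*SAP*

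**What the plan says.** SAP section 3.6.1, Table 5, defines a treatment-emergent adverse event separately for each analysis period.

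- RCP, treatment policy: onset "on or after the first RCP IP dose, and on or before the end of RCP".
- Combined RCP and OLP (Any Inebilizumab Analysis Set), subjects who do not enter the OLP: onset from the first inebilizumab dose "up to and including the day prior to the end of RCP".
- Combined RCP and OLP, subjects who do enter it: the limit is "the end of OLP (i.e., the day prior to the SFP entry, if a subject rolled over to OLP").
- Safety follow-up (SFP): any onset after the last dose of investigational product.

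The text before Table 5 assigns the treatment policy strategy to the combined period. It also says that, for subjects who withdraw from the study, data through the last visit are kept. SAP section 3.1 defines the RCP treatment-policy period as running to the end of Visit 15 (Week 52), inclusive.

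SAP Table 4 (section 3.4.3) runs combined person-years to the "Date of last study day in RCP or" OLP, minus the first inebilizumab dose date, plus 1. Section 3.6.1 uses those person-years for event rates per 100 person-years.

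Protocol section 4.1 fixes the date concerned: "The end of the RCP is defined, per subject, as the date of completion of the Week 52 RCP visit".

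**The concern.** Two columns of one table set different last days for the same subjects over the same period, and the SAP gives no reason. An event can then appear in the RCP summary for the inebilizumab arm and be missing from the overall-exposure summary, which ought to contain it. The rate per 100 person-years would also count a day in the denominator whose events are excluded from the numerator.

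The excluded day is a scheduled visit. Protocol Table 4 places laboratory tests, ECG, weight and a full physical examination at Visit 15, and in the RCP the ECG and full examination occur only at Visits 2, 9 and 15. Protocol section 6.3.3 says clinically important abnormalities in "laboratory parameters, and ECGs will be recorded as AEs or SAEs". It does not say that onset is dated to the visit, but some findings may carry that date.

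At stake are the consistency of two safety tables and an avoidable reconciliation query. No efficacy result and no randomized safety comparison is affected.

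**Working it through.** The plan gives no figure to reproduce here, so the check is of date windows.

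**Inputs.** Take an inebilizumab-arm subject who completes Week 52 and does not enter the OLP. Day 1 is the first dose and the last dose is on Day 183 (protocol Table 4, Visit 9). The end of RCP is nominally Day 365, with a visit window of 7 days either side, so Day 358 to Day 372.

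**Table 5 windows as inequalities.**
- RCP, treatment policy: 1 ≤ onset ≤ end of RCP
- Combined, as written: 1 ≤ onset ≤ end of RCP − 1
- SFP: onset > 183

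| End of RCP | Onset day | RCP | Combined, as written | SFP |
|---|---|---|---|---|
| 358 | 357 | in | in | in |
| 358 | 358 | in | **out** | in |
| 365 | 364 | in | in | in |
| 365 | 365 | in | **out** | in |
| 372 | 371 | in | in | in |
| 372 | 372 | in | **out** | in |

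The mismatch is always the final visit day, whenever the visit falls in its window.

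**Denominator.** With the end of RCP on Day 365, Table 4 gives (365 − 1 + 1)/365.25 = 365/365.25 = 0.99932 person-years. The literal event window covers 364 days, or 364/365.25 = 0.99658 person-years. The difference is one day, 1/365 = 0.27% of the window.

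**After the change.** Ending the combined window at the end of RCP makes it Day 1 to Day 365. A Day 365 onset then counts in both tables, and the window matches the 0.99932 person-years.

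**Is the early stop a hand-off between periods?** It does not work as one. The SFP event window opens after the last dose, so with a last dose on Day 183 it already overlaps the RCP by 365 − 183 = 182 days. Removing one day does not separate the two. A limit of the day before suits the start of a following period, as in the safety follow-up clause of the same cell. Here it is attached to the end of a period, which looks like a drafting slip.

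**The case against.** The strongest reply is that almost nothing is lost, and most of it stands.

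- **Follow-up covers the day.** Subjects who do not enter the OLP go into safety follow-up, so a reader who infers that no other period takes up the missing day would be wrong. A Week 52 onset normally meets the SFP definition as well as the RCP one, and is absent from only one of three summaries.
- **Early withdrawals may already be included.** The sentence keeping data through the last visit can be read as covering the early discontinuation visit. The protocol's end-of-RCP definition refers only to the Week 52 visit and does not strictly apply to these subjects. The conflict is clear only for Week 52 completers.
- **Fatal or treatment-ending events.** A reader might infer that such events disappear. The documents do not support this. SAP section 3.6.1 plans a separate summary of all deaths and listings of all adverse events, treatment-emergent or not. Subjects who stop treatment are to remain in the RCP to Day 365 (protocol sections 4.1 and 6.4.1), so the event that stops dosing would not normally fall on the last RCP day. A Week 52 onset comes after the last RCP dose.
- **Scope.** Subjects who received only placebo are not in the Any Inebilizumab set, so the slip cannot affect them.

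None of this explains why the combined column should stop a day before the RCP column, the section 3.1 period and the Table 4 person-years. The inconsistency stands as a counting rule that would be wrong if programmed as written.

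**Conclusion.** Wrong as written, at the lowest severity. For inebilizumab-treated subjects who complete Week 52 and do not enter the OLP, the literal rule drops final-visit-day onsets from the Any Inebilizumab numerator while keeping the day in the denominator. The size is one day per affected subject, about 0.27% of a 365-day window, and less as a share of the whole set's person-years, which also include OLP time.

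The number of events cannot be estimated from the documents, which give neither the share of subjects who will not enter the OLP nor the chance of an onset dated to the last visit. A reader might guess at 1 to 3 lost events: if 8 to 16 subjects (10% to 20% of 80) do not enter and 10% to 20% of them have such an onset, the product is 0.8 to 3.2. Both rates are assumptions without support. As a rough contrast, 71.8% of inebilizumab subjects in the NMOSD study had an event in a randomized period of about 197 days (protocol section 2.1.5.3). A constant rate gives −ln(0.282)/197 = 0.64% per day, or 0.05 to 0.10 events in 8 to 16 subjects. That is another disease and counts first events only; repeat events and visit-day dating would raise it. The number is likely very small and may be zero.

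The conclusion rests on the literal text of Table 5 and on the protocol's definition of the end of RCP.

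**What to change.** In the combined column of SAP Table 5, for subjects who do not enroll into the OLP, delete the words that move the limit back one day, so that the window ends as in the RCP column: "on or before the end of RCP". This brings the combined column into line with the RCP column, SAP section 3.1 and the Table 4 person-years. The same edit could confirm that the last-visit rule governs early withdrawals, whose end of RCP the protocol does not define.

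The cost is a few words in the SAP and the matching programming specification. No data collection, efficacy analysis or randomized comparison changes.
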